HCG	Human chorionic gonadotrophin
HIPAA	Health Insurance Portability and Accountability Act
HRQL	Health Related Quality of Life, a subscale of the UFS-QOL
ICE	Intracardiac echocardiography
ICF	Informed consent form
ICH	International Conference on Harmonization
INR	International normalized ratio
LAA	Left atrial appendage
LMWH	Low-molecular-weight heparin
LV	Left ventricle
MI	Myocardial infarction
MRI	Magnetic resonance imaging
NYHA	New York Heart Association
PVI	Pulmonary vein isolation
RF	Radiofrequency
SADE	Serious Adverse Device Effect
SAE	Serious Adverse Event
TEE	Transesophageal echocardiogram
TTE	Transthoracic echocardiogram
TIA	Transient ischemic attack
UADE	Unanticipated Adverse Device Effect

3 PROTOCOL SYNOPSIS

Sponsor: Abbott Electrophysiology (Topera, Inc.)

Protocol Title: Randomized Evaluation of Atrial Fibrillation Treatment with Focal Impulse and Rotor Modulation Guided Procedures (REAFFIRM)

Planned Study Centers: Up to 25 centers in Europe and North America

Primary Objective:

Evaluate the safety and effectiveness of FIRM-guided procedures in addition to conventional ablation for the treatment of patients with de novo persistent atrial fibrillation (AF).

Secondary Objectives:

- Evaluate the acute effectiveness of FIRM-guided procedures in eliminating the source of arrhythmia.

Study Design:

This is a prospective, multicenter, randomized study to assess the safety and effectiveness of FIRM-guided procedures followed by conventional ablation including PVI versus a standard PVI procedure for the treatment of de novo persistent atrial fibrillation.

Sample Size:

A total of up to 350 subjects will be enrolled and equally (1:1) randomized between those undergoing conventional AF treatment with ablation, vs. those with FIRM-guided procedures followed by conventional AF ablation. Additionally, ablation of any atrial tachycardias (AT) and/or the cavotricuspid isthmus may be performed in those subjects with documented AT/atrial flutter.

Study Duration:

Subject participation will require up to 13 months. The follow-up assessments will occur at 7-10 days post-procedure, 1, 3, 6, and 12 months post-procedure.

Inclusion Criteria:

Subjects are required to meet the following inclusion criteria:

1. Male or female 18 – 80 years of age.
2. Experiencing at least two (2) documented episodes of persistent atrial fibrillation (including long standing persistent) during the 3 months preceding study entry with clinical indication for AF ablation per guidelines. At least one episode must be documented by rhythm strip or ECG.
3. Refractory, contraindicated, or intolerant to Class I or III anti-arrhythmic medications. Drug doses must be therapeutic and stable.
4. Oral anticoagulation required with either Novel Oral Anticoagulant (e.g. dabigatran, rivaroxaban, apixaban), Warfarin (therapeutic INR ≥ 2.0 for at least three weeks prior to randomization), or other similar standard-of-care oral anticoagulant therapy is required (aspirin is not considered similar) for those subjects who meet two or more of the following criteria:
 - a. Age 65 years or older
 - b. Diabetes
 - c. Coronary artery disease (CAD)
 - d. Congestive heart failure
 - e. Hypertension with systolic >165 mm Hg
5. Willingness and able to remain on anti-coagulation therapy for a minimum of 3 months post procedure for all subjects and at least 12 months post procedure if the patient is on anti-coagulation pre-procedure or has CHADS₂ score ≥ 2 .
6. Left atrial diameter < 6.0 cm via transthoracic echo; or <6.5 cm via CT or MRI up to 3 months pre-procedure with documented image of largest dimension, or intra-procedural ICE or atrial angiogram if CT/MRI not available.
7. Sustained AF (>5 min uninterrupted) during the electrophysiology procedure. If the subject is not experiencing spontaneous, sustained AF, it may be induced by burst pacing (typically, from the coronary sinus) with or without isoproterenol infusion in conventional clinical fashion.
8. Women without childbearing potential, (surgically sterile or have been without a period for 12 months), or women of childbearing potential who are not pregnant per a serum HCG laboratory test.
9. Willingness, ability and commitment to participate in baseline and follow-up evaluations without participation in another clinical trial which may confound the results of this study, unless approved by the Sponsor.
10. Informed consent in writing from patient.

Exclusion Criteria:

Subjects must NOT meet any of the following exclusion criteria:

1. Presence of structural heart disease of clinical significance including:
 - a. Coronary artery disease with either:
 - o Coronary artery bypass surgery (CABG) within the last six months, or
 - o Stable/unstable angina or ongoing myocardial ischemia
 - b. Congenital heart disease where either the underlying abnormality or its correction prohibits or increases the risk of ablation.
2. NYHA Class IV.
3. Ejection fraction < 35% (within previous 3 months).
4. Previous AF ablation.
5. History of myocardial infarction (MI) within the past three months.
6. Any concomitant arrhythmia or therapy that could interfere with the interpretation of the results from this study.
7. ASD closure device, LAA closure device, prosthetic mitral or tricuspid valve, and permanent pacemakers or defibrillator leads.
8. Untreatable allergy to contrast media.
9. Severe electrolyte abnormalities at time of the ablation procedure or atrial fibrillation secondary to electrolyte imbalance, thyroid disease, or reversible non-cardiac cause.
10. Atrial fibrillation from a reversible cause (e.g., surgery, hyperthyroidism, pericarditis).
11. Contraindication to Heparin and Warfarin/other novel oral anticoagulants (e.g. dabigatran, rivaroxaban, apixaban).
12. History of pulmonary embolus within one year of enrollment.
13. Acute pulmonary edema.
14. Atrial clot/thrombus on imaging such as on a trans-esophageal echocardiogram (TEE) performed within 72 hours of the procedure if deemed appropriate by investigator.
15. Any history of a cerebrovascular disease (including stroke or TIA).
16. Any anticipation of cardiac transplantation or other cardiac surgery within the next 12 months.
17. History of documented thromboembolic event within the past one year that affects the ability to perform the procedure.
18. Diagnosed atrial myxoma.
19. Significant pulmonary disease, (e.g. restrictive pulmonary disease, constrictive or chronic obstructive pulmonary disease) or any other disease or malfunction of the lungs or respiratory system that produces severe chronic symptoms and significantly increases risk to sedation or anesthesia.
20. Acute illness or active systemic infection or sepsis.
21. Any history of blood clotting abnormalities or bleeding abnormalities.
22. Life expectancy of less than 12 months.
23. Any intramural thrombus, tumor, or other abnormality that precludes catheter introduction or safe manipulation.

Safety Assessments:

Safety shall be evaluated both acute (in hospital) and long term:

- Acute safety success of either treatment arm is defined as freedom from serious adverse events related to the procedure within 7-10 days of the index procedure.
- Long-term safety is defined as freedom from procedure-related serious adverse events (including those related to repeat procedures) within one year of the index procedure.

Effectiveness Assessments:

- Acute Effectiveness

The acute success of FIRM-guided procedure is defined as elimination of the source of arrhythmia identified by FIRMap as indicated by:

1. No evidence of the source on FIRMap immediately post-procedure, OR
2. Reduction of electrogram amplitude to <0.2mV in region designated by FIRMap.

- Long-term Effectiveness

The long-term effectiveness of FIRM-guided procedures versus conventional ablation shall be defined as:

1. Single-procedure freedom from atrial fibrillation (AF) and atrial tachycardia (AT) recurrence at 3 months.
2. Single-procedure freedom from AF/AT recurrence at 3 to 12 months.

Freedom from AF/AT recurrence is defined as no documented episodes of AF > 30 seconds with conventional non-invasive monitoring. In the case of a cardiac implanted electronic device (CIED), freedom from AF/AT recurrence is defined as no documented episodes of AF > 30 seconds in a 48 to 72-hour window at the follow-up visits in addition to any symptomatic episodes with documented AF > 30 seconds. AT recurrence does not include episodes of CTI (cavotricuspid isthmus) dependent flutter.

Refer to the Statistical Analysis Plan for details.

4 BACKGROUND AND RATIONALE

Atrial fibrillation (AF) is the most common sustained arrhythmia in man, and has an increasing population prevalence over time. Treatment is aimed at stroke prevention on the one hand, and amelioration of symptoms (palpitations, lightheadedness, dyspnea, fatigue) due to the arrhythmia. Medical therapy often fails to render a satisfactory response for the latter, prompting the search for alternative therapies. Surgical and, in the last 15 years, catheter ablation techniques have been devised to try to prevent episodes from starting. Groundbreaking work by Haïssaguerre¹ showed that premature discharges or rapid repeated firing from the pulmonary veins (PVs) could trigger AF episodes and that electrical isolation of the PVs could potentially cure the patient of AF. PV isolation currently is a painstaking process consisting of delivering radiofrequency energy in the left atrium to isolate these veins. Such procedures take 3-5 hrs. to complete depending on the complexity of the individual case, and a majority of patients require a 2nd or even 3rd procedure to achieve acceptable antiarrhythmic results. Despite considerable investigative effort, the exact pathophysiology of how PV triggers initiate and or maintain episodes of AF has been elusive.

Recently, Narayan et al² have developed an algorithm that has been licensed for use with a novel mapping technology (RhythmView, Abbott (Topera, Inc.), Menlo Park, CA) for analyzing atrial recordings during human AF, finding that >95% of cases demonstrate either a rapidly spinning rotor (small circuit) or very rapid focal impulse formation. Furthermore, they have shown that catheter ablation at these relatively circumscribed areas can significantly affect AF, either by substantial slowing of the rate or termination (to an atrial tachycardia or sinus rhythm). In the CONFIRM (CONventional vs Focal Impulse and Rotor Modulation) trial, patients were treated with either conventional mapping and ablation (largely PV isolation or PVI) vs ablation of rotors or sites of focal impulse formation as designated by the mapping algorithm, followed by conventional ablation (PVI). The authors found much higher acute and long-term efficacy when focal impulse and rotor modulation (FIRM procedure) was used (82.4 vs 44% freedom from AF at 24 months post procedure). Although CONFIRM was a controlled study, a randomized evaluation would be warranted.

¹ Haïssaguerre M, Jaïs P, Shah DC et al. Spontaneous initiation of atrial fibrillation by ectopic beats originating in the pulmonary veins. *N Engl J Med* 1998; 339: 659–66.

² Narayan, S.M., D.E. Krummen, P. Clopton, K. Shivkumar and J.M. Miller. Direct Or Coincidental Elimination of Stable Rotors or Focal Sources May Explain Successful Atrial Fibrillation Ablation: On-Treatment Analysis of the CONFIRM (CONventional ablation for AF with or without Focal Impulse and Rotor Modulation) Trial. *Journal of the American College of Cardiology* (2013) 62:138-147.

REAFFIRM is a prospective, multicenter, randomized, controlled study to assess the safety and effectiveness of FIRM procedures followed by conventional ablation including PVI versus a standard conventional procedure including PVI for the treatment of persistent atrial fibrillation.

4.1 RATIONALE

According to the American Heart Association, atrial fibrillation affects approximately 2 million Americans. Atrial fibrillation may reduce cardiac performance and may result in thrombus formation in the left atrium and thromboembolic events, such as stroke. Approximately 15% of all strokes occur in people with atrial fibrillation. Ablation of atrial fibrillation that specifically targets approximately 2-3 mm outside of the pulmonary vein is currently a standard of care treatment in subjects with symptomatic atrial fibrillation who have failed drug therapy. Unfortunately, this procedure is time consuming, creates substantial damage in the left atrium due to the number of lesions required, and has mixed success with the best outcomes being 50-70% freedom from symptoms at 1 year post ablation. Also, as with any invasive procedure, patient complications may heighten with increased time and additional radiation exposure.

One of the major issues with the current procedure is the lack of knowledge about the critical regions of the heart that have the source rhythms causing and sustaining AF. Some very new technology developed based upon work done under NIH support at the University of California San Diego has shown promise in diagnosing these key source rhythms. Ablation to target these sources, called Focal Impulse and Rotor Modulation (FIRM) guided procedure, shows promise but need to be evaluated further.

4.2 HYPOTHESIS

Focal Impulse and Rotor Modulation (FIRM) guided procedures will eliminate the source of clinical arrhythmias in subjects with indications for AF ablation procedures.

5 **STUDY OBJECTIVES**

The primary objective is to evaluate the safety and effectiveness of FIRM procedures in addition to conventional ablation for the treatment of persistent atrial fibrillation (AF).

The secondary objectives are: 1) to evaluate the acute success of FIRM-guided procedure in eliminating the source of arrhythmias, and 2) to evaluate quality of life outcomes.

6 **STUDY DESIGN**

The study is designed as a prospective, multicenter, randomized study to assess the safety and effectiveness of FIRM procedures followed by conventional ablation including PVI versus a standard PVI procedure for the treatment of de novo persistent atrial fibrillation.

6.1 SAMPLE SIZE

A total of up to 350 subjects at up to 25 investigative sites will be enrolled and equally (1:1) randomized between those undergoing conventional AF treatment with ablation, vs. those with FIRM-guided procedures followed by conventional AF ablation. Additionally, ablation of any atrial tachycardias (AT) and/or the cavitricuspid isthmus may be performed in those subjects with documented AT/atrial flutter.

6.2 RANDOMIZATION

Block randomization using a web-based database system will be used to assign subjects (1:1) to the conventional AF ablation treatment without FIRM-guided diagnostic procedure, or to the FIRM-guided procedure followed by conventional AF ablation.

6.3 STUDY DURATION

Overall study duration (first subject enrolled through last subject exit) will be comprised of approximately 18 months of enrollment period, 1 month per subject for screening and baseline measurements, and 12 months per subject for follow-up, for a total study duration of up to 31 months. Study duration for an individual subject, once consented, will be up to 1 month for screening (including baseline measurements) and 12 months for follow up after treatment for a total duration of approximately 13 months.

7 ENDPOINTS

7.1 PRIMARY SAFETY ENDPOINTS

Safety shall be evaluated both acute (in hospital) and long term.

Table 1 – Primary Safety Endpoints

Endpoint	Description
Acute success	Freedom from serious adverse events related to the procedure within 7-10 days of the procedure.
Long-term success	Freedom from procedure-related serious adverse events (including those related to repeat procedures) within one year of the initial procedure.

7.2 PRIMARY EFFECTIVENESS ENDPOINTS

Effectiveness endpoints are defined in the table below.

Table 2 – Primary Effectiveness Endpoints

Endpoint	Definition
Long term success	
Dual endpoints will be used for long term effectiveness after the initial AF ablation procedure (only):
 
(1) Single Procedure Freedom from AF/AT recurrence* at 3 months, or
 
(2) Single Procedure Freedom from AF/AT recurrence* from 3-12 months after the initial AF ablation procedure.
 
* Freedom from AF/AT recurrence is defined as no documented episodes of AF > 30 seconds with conventional non-invasive monitoring. In the case of a cardiac implanted electronic device (CIED), freedom from AF/AT recurrence is defined as no documented episodes of AF > 30 seconds in a 48 to 72-hour window at the follow-up visits in addition to any symptomatic episodes with documented AF > 30 seconds. AT recurrence does not include episodes of CTI (cavotricuspid isthmus) dependent flutter.

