7.3 SECONDARY ENDPOINTS

Secondary endpoints are defined in Table 3 below. This study will also collect data relating to the health economics of the FIRM-guided procedure to conduct additional evaluations if primary endpoints are met.

Table 3 – Secondary Endpoints

Endpoint	Definition
Acute Effectiveness	
The acute success of FIRM-guided procedure is defined as elimination of the source of arrhythmias identified by FIRMap as indicated by;
 
 1. No evidence of the source on FIRMap immediately post-procedure, OR 2. Reduction of electrogram amplitude to <0.2mV in region designated by FIRMap

Table 4 – Additional Evaluations

Parameter	Definition
Total RF ablation time	Total RF ablation time as measured by total time of ablation lesion applications, from first ablation lesion to end of last lesion, will be documented. These values will be compared between the FIRM-guided and conventional ablation groups. If ablation for AT/atrial flutter is pursued, this ablation time will be documented separately
Repeat procedure and hospitalization	Any descriptive information regarding repeat procedures and re-hospitalizations will be compared between groups
Cumulative long-term freedom from AF	Cumulative long-term freedom from AF will be assessed at 12 months after the initial AF procedure but will permit results of repeat ablation
Cumulative long-term freedom from AF without use of anti-arrhythmic drugs	Cumulative long-term freedom from AF without use of anti-arrhythmic drugs will be assessed at 12 months after the initial AF procedure but will permit results of repeat ablation
Early Recurrence of AF/AT	Recurrences of sustained AF/AT in the first 3 months (blanking period).
Change in Atrial Function	Change in left atrial size and pulmonary vein inflow Doppler on echocardiogram (when available)
Change in Ventricular Function	Change in left ventricular ejection fraction and parameters of diastolic dysfunction (when available)
Quality of Life	Impact on quality of life, using patient-reported outcome instruments (EQ-5D and AFEQT), within treatment groups (change from pre-procedure to post-procedure follow-up timepoints) and between treatment groups. Analysis will be performed if primary endpoints are met.
Economic Analysis	Cost-effectiveness analysis based on clinical and patient-reported outcomes and resource utilization. Analysis will be performed if primary endpoints are met.

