10.3 FOLLOW-UP REQUIREMENTS

- ***Follow-Up Visit Schedule***

Each enrolled subject will return for visits with the electrophysiologist in accordance with Table 8 below. The day of the study procedure represents Day 0. Study visits that do not occur within the below time windows will be considered protocol deviations.

Table 8 Follow-up (FU) Visit Windows

Visit	Allowed Visit Date Range
Day 7 to 10 days (Phone or visit)	N/A
1 month (30 days)	± 1 week
3 months	± 2 weeks
6 months	± 2 weeks
12 months	± 4 weeks

- ***Resolution Period***

Following ablation treatment, subjects will undergo a 90-day "resolution" period (aka "blanking period") where medical therapy may be optimized and where any of the procedurally-derived arrhythmias that commonly follow ablation procedures may resolve.

Note: During the 90-day resolution period, medications may be adjusted as medically indicated, and as indicated in above section. Any clinically indicated changes must be documented along with the reason for change.

- ***Anti-arrhythmic Medications***

Anti-arrhythmic medications can be discontinued anytime from Day 91 to Day 180 post-procedure. The date of discontinuation will be determined by each investigator on a patient-by-patient basis, but must occur sometime from Day 91 to Day 180 post-procedure.

- ***Recurrence of AF***

If re-ablation for AF is necessary after documentation of the recurrent arrhythmia has occurred, the patient will be considered a primary efficacy study failure but still followed up for AF burden.

A. Day 7-10 Days Follow-up

(Phone Call or visit at investigator's discretion)

- Subjects will be asked if they have experienced any untoward medical occurrences since the study procedure. If so, these events will be recorded on the Adverse Event form.
- Symptom and rhythm assessment.

B. One-Month Follow-up (± 1 week)

The following assessments/procedures will be performed:

- Diagnostic 12-lead ECG
- At least 24-hr ambulatory continuous ECG monitor (Holter) or CIED interrogation, if applicable
- EQ-5D and AFEQT Quality of Life surveys
- Symptom and rhythm assessment
- Concomitant anti-arrhythmic medications
- Adverse event documentation

C. Three-Month Follow-up (+ 2 weeks)

The following assessments/procedures will be performed:

- Diagnostic 12-lead ECG

- At least 24-hr ambulatory continuous ECG monitor (Holter) or CIED interrogation, if applicable
- EQ-5D and AFEQT Quality of Life surveys
- Symptom and rhythm assessment

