16.2 Study Endpoints

A. Long-Term Effectiveness (Primary effectiveness endpoint)

Two endpoints will be used for long term effectiveness after the initial AF ablation procedure (only):

Single Procedure Freedom from AF/AT recurrence* at 3 months, and

Single Procedure Freedom from AF/AT recurrence* from 3-12 months after the initial AF ablation procedure.

Freedom from AF/AT recurrence is defined as no documented episodes of AF > 30 seconds with conventional non-invasive monitoring. In the case of a cardiac implanted electronic device (CIED), freedom from AF/AT recurrence is defined as no documented episodes of AF > 30 in a 48 to 72-hour window at the follow-up visits in addition to any symptomatic episodes with documented AF > 30 seconds. AT recurrence does not include episodes of CTI (cavotricuspid isthmus) dependent flutter.

The statistical hypothesis for this endpoint is operationalized as follows:

$H_0: p_E = p_C$

$H_A: p_E \neq p_C$

$\alpha =$ [REDACTED]

Where:

p_E = the proportion of "successes" in the FIRM arm

p_C = the proportion of "successes" in the conventional ablation control arm

The proportion of successes in each treatment arm shall be evaluated relative to their respective primary endpoint using both Chi-Square (Binomial, 1df) and by Kaplan-Meier survival estimation. Each evaluation will include 95% confidence intervals. Since there are multiple (dual) independent endpoints, each resulting p-value will be reported both as calculated, and the associated Hochberg corrected p-value.

B. Acute Effectiveness (Secondary effectiveness endpoint)

The acute success of FIRM-guided procedure is defined as elimination of the source of arrhythmias identified by FIRMap as indicated by;

1. No evidence of the source on FIRMap immediately post-procedure, OR
2. Reduction of electrogram amplitude to <0.2mV in region designated by FIRMap

The proportion of successes in each arm will be calculated as follows:

$$\frac{n}{N}$$

Where:

n = the total count of "successful" subjects in the arm in question

N = the total count of subjects for that arm in the ITT group

The statistical hypothesis for this endpoint is operationalized as follows:

$$H_0: p_E = p_C$$

$$H_A: p_E \neq p_C$$

$$\alpha = \text{[REDACTED]}$$

Where:

p_E = the proportion of "successes" in the FIRM arm

p_C = the proportion of "successes" in the conventional ablation control arm

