16.3 INTERIM ANALYSIS

An interim analysis will be conducted on the 12-month primary effectiveness endpoint when 100 patients in each arm have achieved a full 12 months' follow-up from the index ablation procedure.

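### Table 2, the synopsis and section 16.2 file a 3-month result under long-term effectiveness, and the success rule lets it win alone, so a long-term claim could be made with no 3–12 month benefit

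*Protocol*

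**What the plan says.** Three places in the protocol define the primary effectiveness endpoints.

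- **Synopsis (section 3), long-term effectiveness:** a two-item list with no connector. The first item is "Single-procedure freedom from atrial fibrillation (AF) and atrial tachycardia (AT) recurrence at 3 months"; the second is freedom from recurrence at 3 to 12 months.
- **Section 7.2, Table 2:** a single row for long-term success, introduced as dual endpoints. Its first limb reads "Single Procedure Freedom from AF/AT recurrence* at 3 months, or" and its second is the 3–12 month result.
- **Section 16.2 A, headed as long-term effectiveness:** "Single Procedure Freedom from AF/AT recurrence* at 3 months, and" the 3–12 month result. The multiplicity rule follows: "Since there are multiple (dual) independent endpoints, each resulting p-value will be reported both as calculated, and the associated Hochberg corrected p-value".

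Other sections treat the first three months differently. Section 10.3 sets a 90-day resolution or blanking period "where any of the procedurally-derived arrhythmias that commonly follow ablation procedures may resolve". Section 7.3, Table 4, lists recurrence in the first 3 months, which it identifies as the blanking period, only among the additional evaluations. Section 16.3 looks only at the later endpoint: "An interim analysis will be conducted on the 12-month primary effectiveness endpoint". For quality of life and for the economic analysis, Table 4 says "Analysis will be performed if primary endpoints are met".

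**The concern.** A reader of the final report will take long-term effectiveness to mean benefit that lasts beyond the healing period. The protocol gives that name to a set of two endpoints, one of which is reached at about the end of that period. It also adopts a rule under which that endpoint can succeed without the other. No passage makes the 3–12 month result a condition of the long-term claim. The interim analysis suggests that the later endpoint leads, but Table 2 and section 16.2 give it no precedence.

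At stake is the headline conclusion on the trial's primary objective. A real but short-lived advantage at 3 months could be reported, in line with the plan, as long-term success. The condition that releases the quality-of-life and economic analyses has a related gap: the text does not say which endpoints have to be met. It speaks of primary endpoints in the plural, and Table 1 also names two primary safety endpoints.

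**Working it through.** **Step 1: what the rule allows.** For two endpoints, Hochberg declares both if the larger p-value is ≤ α. Otherwise it declares the endpoint with the smaller p-value if that p-value is ≤ α/2. Either endpoint can therefore win alone, as Table 2's *or* also allows. The *and* in section 16.2 closes the first item of a list introduced as two endpoints. It does not say that both must succeed.

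**Step 2: where the 3-month result sits in time.** The protocol does not say whether *at 3 months* means all events since Day 0 or status at the visit.
- All events since Day 0: the interval is essentially the 90-day blanking period.
- Status at the visit, taking 3 months as Day 90: Table 8 allows ± 2 weeks, so Day 90 − 14 = 76 to Day 90 + 14 = 104. The visit heading in section 10.3 gives only + 2 weeks, so Day 90 to 104. The reading is near the end of blanking and may fall on either side of it.

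Neither reading describes the 3–12 month period.

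**Step 3: is type I error affected?** α is redacted, so two-sided 0.05 is assumed. The two test statistics are taken as bivariate normal with correlation 0 to 0.7, and the interim look is left out. With no effect on either endpoint, Hochberg declares at least one in 5.0% of trials at correlation 0, falling to about 4.5% at 0.7. Unadjusted testing of two independent endpoints would give 1 − 0.95² = 9.75%. The pair is controlled, provided the corrected p-values decide.

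**Step 4: how often would the 3-month endpoint win strictly alone?** Assume a true 3-month effect and no 3–12 month effect. A win strictly alone means that the 3-month endpoint is declared in favour of FIRM and the 3–12 month endpoint is not declared in either direction. At correlation 0 this is

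P(alone) = P(3-month p ≤ 0.025, favourable) × P(3–12 month p > 0.05) = Φ(z₀.₉₇₅ + z_power − z₀.₉₈₇₅) × 0.95,

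with z₀.₉₇₅ = 1.960 and z₀.₉₈₇₅ = 2.241. The last column comes from simulation.

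| 3-month power at full α | Favourable, p ≤ 0.025 | × 0.95 (correlation 0) | Correlation 0 to 0.7 |
|---|---|---|---|
| 50% | 0.389 | 0.370 | 0.365–0.370 |
| 80% | 0.712 | 0.677 | 0.677–0.685 |
| 90% | 0.841 | 0.799 | 0.799–0.811 |

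**Step 5: what differences those powers represent.** Up to 350 subjects at 1:1 (section 6.1) gives 175 per arm. Assume 50% success in the control arm. With p̄ the mean of the two proportions,

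power = Φ{[d − 1.96√(2p̄(1 − p̄)/n)] / √(p_E(1 − p_E)/n + p_C(1 − p_C)/n)}.

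For d = 0.15: [0.15 − 1.96 × 0.0528] / 0.0522 = 0.889, so power is 0.813. In the same way, d = 0.105 gives 0.506 and d = 0.17 gives 0.901. The three rows correspond to 3-month differences of about 10.5, 15 and 17 points.

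**Step 6: the same case with the 3–12 month result required.** Hochberg never declares an endpoint whose p-value exceeds α. With no 3–12 month effect, a favourable long-term claim would then occur in at most 2.5% of trials.

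**The case against.** The strongest reply has five parts.

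1. **The connectors do not conflict.** A reader might infer from *or* in Table 2 and *and* in section 16.2 that the protocol states two rival decision rules. The text does not support that. Both words join items in a list, and Hochberg agrees with *or*. This part stands: the difference is one of wording. It also means that changing *or* to *and* would leave the problem in place.

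2. **The success rule may be in the SAP.** The synopsis refers to the SAP for details, and α and section 16.4 are redacted. This is fair, and the absence of further detail is not the point here. The protocol itself fixes the long-term label and a procedure under which the 3-month endpoint can carry it alone.

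3. **Both results will be seen.** Section 16.2 reports each p-value, and each endpoint carries its time frame in its name. That limits the harm to a careful reader. It does not stop a conclusion of long-term effectiveness that the plan's wording would permit.

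4. **The 3-month visit can fall after blanking, and the illustration assumes its scenario.** Both are correct. A visit up to about Day 104 is possible, and on the visit-status reading the early-recurrence item in Table 4 is a different quantity. The endpoint remains an early one. The percentages show that a win on 3 months alone is no rare accident where there is a real early effect; they do not forecast this trial.

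5. **Hochberg is valid.** A reader might infer that the procedure is wrong and must give way to a fixed sequence. The documents do not support that. Replacing it is a design trade-off against a sample-size basis that cannot be seen.

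**Conclusion.** The point holds as a defect of labelling and of what the claim means. Following the protocol exactly, a long-term effectiveness claim could rest on the 3-month result with no 3–12 month benefit. In the illustration this happens in about 36–37%, 68–69% and 80–81% of trials at 3-month powers of 50%, 80% and 90%. Most of these would be true 3-month findings under the wrong name.

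A reader might also infer an inflated false-positive rate. That is not supported: across the pair the rate stays at or below the assumed 5%.

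The figures rest on an assumed two-sided α of 0.05, correlation 0 to 0.7, no 3–12 month effect, no interim look and, for the point differences only, 175 per arm with 50% control success. The textual finding depends on none of these. Any effect on the planned power of the 3–12 month test cannot be judged, because α and section 16.4 are redacted. The matter should be corrected; confidence is medium, because the SAP is not at hand.

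**What to change.** In the synopsis, Table 2 and section 16.2:

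- use one wording for the pair;
- label the 3-month endpoint as early rather than long-term effectiveness;
- state that a long-term effectiveness claim requires the 3–12 month endpoint to be significant, after the multiplicity correction, in favour of FIRM.

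In the same edit, state in section 7.3 and Table 4 which endpoints must be met before the quality-of-life and economic analyses are done, and whether the safety endpoints count.

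Hochberg can stay. Testing 3–12 months first in fixed sequence, or making the 3-month endpoint secondary, is an option for the sponsor to weigh and not a required correction. In the illustration with both effects at 80% power, the fixed sequence lowers the chance of at least one win from 0.833–0.925 to 0.800, and the chance of a 3-month win from 0.773–0.782 to 0.640–0.713. In return, the 3–12 month test always has full α. If the redacted sample size counted on a win at either endpoint, it would need rechecking under that option.

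The required edit costs a protocol amendment with the approvals in section 13.1 and matching SAP text. No new visits or data are needed. What the sponsor gives up is the right to call a win at 3 months alone long-term effectiveness.
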